5.8. Endpoints

Primary

The measurement of quality in comparison of the modified versus non-modified CCTA using a qualitative (four point scale and measure above) and quantitative (CCTA signal, noise, contrast to noise ratio) score.

Secondary

1. Any changes in the cardiac CT after evaluation of the modified or standard calcium scoring. These changes include: a change in mA by 50, any change in kV, any changes in padding and changing to high definition
2. The measurement of radiation exposure as DLP/milli-sieverts in comparison of the modified versus standard calcium scoring.
3. The measurement of radiation exposure difference measured as DLP/milli-sieverts of the entire CCTA study on the modified versus standard calcium scoring.
4. Whether the imager cancels the study based off of the modified or standard calcium scoring.

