At the conclusion of the CCTA, the patient, in accordance with standard lab procedures, will be clinically assessed and then transported to the cardiology preparation and recovery area (or inpatient ward, as appropriate. Further care will be in accordance with CCTA standard policies.

CCTA Interpretation and Review:

Non-contrast Computed Tomography (calcium scanning)

Calcium scores performed will be scored in typical fashion using the Agatston scoring method¹¹. The total number of lesions, location (coronary artery), and segment (18-segment model) will be recorded.

Scans performed using the modified calcium scan parameters will be assessed in the following manner:

1. No evidence of coronary calcification
2. Number of segments with visible calcification
3. Severity of calcification: small (<5 mm diameter), moderate (5-10 mm), large (>10 mm or circumferential)
4. Location (segment involved)

In all studies, mean image noise will be assessed as the standard deviation of HU within a 1 cm radius region of interest placed in the middle of the proximal ascending aorta, away from aortic valve and aortic tissue. All calcium scores will be interpreted in a random fashion by two trained readers ([name]). Discrepancies will be resolved by consensus.

CCTA

CCTA studies for both the modified and standard calcium scoring reconstructions will be clinically interpreted by the assigned cardiologist and radiologist, in accordance with standard practice. These results will be provided to the patient and referring provider and reported in the health record in standard fashion. The clinical interpretation team will provide an overall assessment of image quality in the following manner: 1-4 (same scale).

In addition to clinical interpretation, all CCTA studies will be read by two experienced CCTA providers ([name]) while blinded to group allocation. All data sets will be assigned a study ID and will be randomly assigned for interpretation. CCTA interpretations will be performed using all available phases. Coronary arterial segments will be graded for quality (see below), stenosis severity (none; <25%, 25-49%, 50-69% and greater than or equal to 70% or 100%), plaque presence, plaque type (non-calcified, partially calcified, mixed). Differences will be adjudicated by consensus. Interpretation of CCTAs will allow for use of any and/or all image reconstruction methods, including axial slices, multiplanar reformats, and maximum intensity

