projections. CCTA image quality will be assessed on a per-segment basis using the 18-segment SCCT model. Image quality will be assessed on a per-segment basis using the following 4-point scale:

Score 1: Non-diagnostic: Impaired image quality that precluded appropriate evaluation of the coronary arteries due to severe motion artifacts, extensive coronary calcifications, severe image noise, or insufficient contrast.

[figure not shown]
Score 2: Adequate: Reduced image quality because of artifacts due to motion, image noise or low contrast attenuation, but sufficient to rule out significant stenosis.

Score 3: Good: Presence of artifacts caused by motion, image noise, coronary calcifications or low contrast, but fully preserved ability to assess the presence of luminal stenosis as well as the presence of calcified and non-calcified coronary atherosclerotic plaque.

[figure not shown]
Score 4: Excellent: Complete absence of motion artifacts, strong attenuation of vessel lumen and clear delineation of vessel walls, with the ability to assess luminal stenosis as well as plaque characteristics.

The overall patient study quality will be determined by the mean of these scores after reaching consensus. In addition, CCTA signal (mean CT number, Hounsfield unit [HU]), noise (standard deviation in HU) and contrast/noise

The two readers will measure the signal and noise in the aortic root and each of the proximal coronary arteries with the mean of the readers used for comparisons. The contrast to noise will also be evaluated (difference of the mean arterial/aorta signal divided by the mean noise). *✓ this*

Flow sheet

5.5.1 Describe when, where and how the study subjects will be identified and recruited.

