5.7.1 Data Analysis Table

Aim 1- To assess the impact on CCTA image quality using modified calcium score approach.	
 - Image quality (4 point scale) - Signal/noise ratio 	
 - Treatment group - Treatment group 	
 - Two sample t-test or Mann-Whitney (dependent upon the distribution of the data). - Two sample t-test
Aim 2- To determine the rate of changes in the coronary CT angiography acquisition parameters of the modified versus standard calcium scoring	
 - Change in (increase or decrease) in tube current (mA) by 50 - Any change in tube potential (kV) - Change to/from retrospectively-gated CCTA - Any change in padding (acquisition window) - Changing to/from a high definition CT acquisition 	
 - Treatment group 	
 - Fisher's exact test

	All answered as yes/no		
Aim 3- To assess the difference in patient estimated effective radiation exposure (mSv) between the modified versus standard calcium scoring techniques.	- Average of radiation exposure (mSv)	- Treatment group	- Two sample t-test
Aim 4- To assess the difference in patient estimated effective radiation exposure (mSv) of the entire CCTA study (plus calcium scoring) between groups.	- Average of radiation exposure (mSv)	- Treatment group	- Two sample t-test

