5.7.2 Sample Size Estimation

The proposed sample size is 158 based on sample size calculations for aim 1, as described below.

Power and sample size for aim 1 is based on a standard deviation of radiation exposure of 3 to 3.5 mSv, based on clinical experience, and an anticipated 40% reduction in exposure from 4 to 2.4 mSv. A sample size of 154 (77 per group) will have 80% power to detect a difference in radiation exposure of 1.6 mSv if the standard deviation is 3.5, based on a t test for independent samples with a 5%, two-sided significance level.

Examining power analyses for a noninferiority studies, assuming that the full and reduced methods will produce similar outcomes for image quality and any change in CCTA parameters:

--For the comparison of image quality (aim 1), it is assumed that the image quality for the full method will be 3.2 (standard deviation = 1.1). This study will have power of 80% to show that the mean for the reduced method is at least as high as the mean for the full method. This assumes that the mean image quality scores for the full and reduced populations are 3.20 and 3.15 respectively, with a common within-group standard deviation of 1.10, that a difference of 0.49 points or less is unimportant, that the sample size in the two groups will be 79 and 79, and that

alpha (1 tailed) is set at .05. To accrue complete data 158 subjects, a total of sample size of up to 175 will be recruited to account for a 10% dropout rate for technical difficulties.

--This study will have 81% power to show that the event rate (event rate = any change in CCTA parameters) for the reduced method is at least as low as the event rate for the full method. This assumes that the event rates for the full and reduced method populations are precisely equal (at 50.0%), that a difference of 20% points or less is unimportant, that the sample size in the two groups will be 79 and 79, and that alpha (1 tailed) is set at .05.

While a 20% difference is relatively large, to detect a smaller difference between groups (i.e. difference of 10-15%) using the same assumptions, would require hundreds of subjects.

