5.7.3 Data Analysis Plan

1. A patient flow diagram as per CONSORT guidelines will be provided to present the number of subjects recruited, screened, refusals or subjects excluded (with reasons), randomized, lost to follow up, etc. Beginning and ending months of recruitment will be described.
2. A table of baseline demographic and clinical characteristics will be presented for the full and reduced scan groups to include means with standard deviations for continuous normally distributed variables, medians with interquartile ranges for ordinal data and counts with percentages for categorical data. Groups may be compared using two sample t-tests, Wilcoxon rank sum tests or Fisher's exact test as appropriate.
3. Interrater reliability for quality scores will be examined using the Kappa statistic.
4. Univariate comparison of the primary and secondary endpoints are described above in the Data Analysis table.
5. Multivariate analysis of the quality score will include ordinal regression, with the concensus quality score (on a scale from 1 to 4) as the dependent variable and the independent variables to include demographic and clinical factors known to affect CCTA quality, such as BMI, breath-holding, resting heart rate, use of nitroglycerin, etc.

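### The Aim 1 tests in 5.7.1 match neither the primary endpoint declared in 5.8 nor the noninferiority comparison powered in 5.7.2, and the variable that decides Aim 1 is implied but not declared.

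*Combined protocol and SAP*

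**What the plan says.** All references are to the combined protocol and SAP.

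- **5.8, primary endpoint.** Image quality, compared between the modified and standard arms "using a qualitative (four point scale and measure above) and quantitative (CCTA signal, noise, contrast to noise ratio) score". That makes four components: the score, signal, noise and contrast-to-noise ratio (CNR).
- **5.7.3, item 4.** "Univariate comparison of the primary and secondary endpoints are described above in the Data Analysis table".
- **5.7.1, Aim 1 row.** Two outcomes. The first is the four-point score, tested by "Two sample t-test or Mann-Whitney (dependent upon the distribution of the data"). The second is "Signal/noise ratio", tested by a two-sample t-test. The row gives no margin, confidence bound, test level or sidedness.
- **5.7.2.** The opening sentence attributes the proposed 158 subjects to the Aim 1 calculation. The next paragraph begins "Power and sample size for aim 1 is based on a standard deviation of radiation exposure of 3 to 3.5 mSv" and arrives at 154. A later bullet, also tagged aim 1, treats the image quality score as a noninferiority comparison. It assumes means of 3.20 and 3.15 and an SD of 1.10, states "that a difference of 0.49 points or less is unimportant", and uses 79 per group, one-tailed 5% and 80% power.
- **5.5, interpretation and review.** Two blinded readers grade each segment from 1 to 4. "The overall patient study quality will be determined by the mean of these scores after reaching consensus".

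**The concern.** A reader who follows the plan from endpoint to test does not reach the declared primary endpoint. CNR is primary in 5.8 and has no test. Signal and noise enter only through a ratio that 5.8 does not list. The score appears in both places, but the test attached to it is a test of difference, while the sample size rests on excluding a loss of 0.49 points.

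The second gap matters more. The question is whether the modified scan preserves CCTA quality, and 6.2 acknowledges that it may reduce accuracy. A difference test without a margin cannot answer that: a non-significant result is compatible with a loss that the 0.49 margin has not excluded. The 80% power in 5.7.2 therefore does not describe the analysis in 5.7.1. Nor does the plan say what Aim 1 concludes if the score and the signal/noise ratio point in different directions.

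**Working it through.** **Endpoint against test**

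| Variable | Primary in 5.8 | Test in 5.7.1, Aim 1 | Margin and power in 5.7.2 |
|---|---|---|---|
| Four-point score | yes | t-test or Mann-Whitney, no margin | noninferiority, 0.49, 80% |
| Signal | yes | only within a ratio | none |
| Noise | yes | only within a ratio | none |
| CNR | yes | none | none |
| Signal/noise ratio | not named | t-test | none |

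**Inputs, all from 5.7.2.** n = 79 per group, SD = 1.10, margin = 0.49, planned true deficit = 3.20 − 3.15 = 0.05, one-sided alpha 5%. The level of the tabled test is not stated, so both two-sided 5% and one-sided 5% are shown. The second is the only level the plan gives for this comparison.

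**1. Reproduce the stated power.** SE = 1.10 × √(2/79) = 0.1750, df = 156. Noncentrality = (0.49 − 0.05)/0.1750 = 2.51. Power from the noncentral t at one-sided 5% = 80.5%, against 80% stated. The arithmetic in 5.7.2 is sound.

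**2. What each test requires of the observed deficit** (at SD 1.10)

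- Noninferiority shown: below 0.49 − 1.655 × 0.1750 = 0.200.
- t-test non-significant, two-sided 5%: up to 1.975 × 0.1750 = 0.346.
- t-test non-significant, one-sided 5%: up to 1.655 × 0.1750 = 0.290.

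An observed deficit between 0.20 and 0.35 (or 0.29) is non-significant without showing noninferiority.

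**3. How often that happens.** The probability equals P(noninferiority not shown) − P(significantly worse), because with these inputs the two favourable and unfavourable outcomes practically never occur together.

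| True deficit | Noninferiority shown | Non-significant without noninferiority, two-sided | Same, one-sided |
|---|---|---|---|
| 0.05 (plan) | 80.5% | 15% | 11% |
| 0.20 (assumed) | 50.2% | 29% | 19% |

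Worked example, one-sided, at 0.05: (1 − 0.805) − (1 − 0.913) = 0.195 − 0.087 = 0.108. At 0.20: (1 − 0.502) − (1 − 0.694) = 0.498 − 0.306 = 0.192. The two-sided figures were confirmed by simulation.

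**4. At a true deficit equal to the margin (0.49).** The t-test is non-significant in 20.5% of trials (two-sided) or 12.7% (one-sided). The noninferiority test wrongly succeeds in 5%.

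**5. Which variable leads.** 79 + 79 = 158 matches the proposed sample size, and the bullet that uses it is tagged aim 1. The radiation calculation gives 77 + 77 = 154. Radiation is Aims 3 and 4 in 5.7.1 and secondary in 5.8. The aim 1 tag on that calculation is therefore a label error.

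**6. Sensitivity of the sample size to the SD.** With 79 per group and otherwise the same inputs, noninferiority power is 96% if the SD is 0.8 and 68% if it is 1.3 (both assumed values).

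**The case against.** The strongest reply is that the intent can be recovered. Section 5.7.2 frames the score as noninferiority, it is the only image measure with a margin and power, and its 158 subjects are the trial's sample size. A t-test can carry a margin, and no passage says a non-significant result will be reported as preserved quality. Most of this stands. A reader might infer that the plan gives no clue to what decides Aim 1, or that the sponsor intends to read non-significance as equivalence. The documents support neither. What remains is that 5.8 and 5.7.1, the sections that fix the endpoint and its test, do not say what 5.7.2 implies.

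A reader might also infer a specific inflation of the false-positive rate, or a loss of joint power, from several unranked primary variables. The plan states no rule under which any one result suffices or all must succeed, and gives no power for the signal/noise ratio, so no such figure can be attached to it.

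The score may also seem to exist in two competing versions, because in 5.5 "The clinical interpretation team will provide an overall assessment of image quality in the following manner: 1-4 (same scale"). That sentence belongs to routine clinical reporting. Section 5.5 defines overall quality as the mean of the consensus segment scores, 5.7.3 refers to the consensus score, and no analysis section uses the clinical rating. This needs clarification only.

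Finally, the size depends on sidedness: the one-sided case is about a quarter to two fifths smaller than the two-sided one. The problem persists in both.

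**Conclusion.** The point holds in this form. The Aim 1 row omits part of the declared primary endpoint, adds a variable that 5.8 does not name, and tests the score without the margin on which the 80% power rests. The deciding variable can be inferred but is not declared. The defect is in the specification of the analysis; the sample size arithmetic is correct.

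Under the planned assumptions, a tabled t-test would be non-significant without noninferiority being shown in 11% to 15% of trials, rising to 19% to 29% if the true deficit were 0.20. These figures assume approximately normal score means, SD 1.10, 79 complete subjects per group, and a 5% test that is either one- or two-sided. They describe the t-test; the Mann-Whitney alternative was not quantified, and it too is tabled without a margin. The plan should be corrected before the image quality data are analysed.

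**What to change.** - **5.7.1.** Replace the Aim 1 score test with a noninferiority test of the patient-level mean of the blinded consensus segment scores. Compare the one-sided 95% confidence bound for the difference in means with the 0.49 margin in 5.7.2. Keep Mann-Whitney as supportive only.
- **5.8.** Declare this score as the variable that decides Aim 1.
- **5.7.1 and 5.8.** Use one identical list of quantitative measures (signal, noise, signal/noise ratio, CNR). Label them supportive unless the sponsor supplies margins and a rule for combining them.
- **5.7.2.** Correct the aim 1 label on the radiation calculation, and confirm that the SD of 1.10 describes the patient-mean score.
- **Clarifications only.** State in 5.5 that the clinical team's rating is not the primary score, and write out the CNR formula in full.

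The cost is wording in these sections and no new measurements. The 158 complete and up to 175 recruited are unchanged only if the SD of 1.10 applies to the patient-mean score; otherwise the power must be recalculated. The downside is that the quantitative measures no longer decide the primary result, which is the sponsor's choice to make.

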- 12) Inability to comply with study procedures
- 13) Prior coronary artery calcium score and/or coronary CT angiogram

DURATION OF STUDY ENROLLMENT: 12 months

SAMPLE SIZE (total enrollment): 175 subjects

3. OBJECTIVES AND SPECIFIC AIMS:

Prior to undergoing CCTA, non-contrast CT scanning of the entire heart is usually performed in adults over 50-years of age in order to assess for the presence and severity of coronary artery calcium. By providing a modified CT scan with a reduced length the same data can be obtained by the imager to ensure a high quality scan while decreasing the patient's overall radiation exposure. Our objectives and specific aims to validate our hypothesis include:

- To assess the impact on CCTA image quality using modified calcium score approach
- To determine the rate of changes in the coronary CT angiography acquisition parameters after evaluation of the modified versus standard calcium scoring scout series. Significant changes in CCTA acquisition include any of the following as compared to recommended CCTA parameters prior to scout CT performance: a change (increase or decrease) in tube current (mA) by 50, any change in tube potential (kV), change to/from retrospectively-gated CCTA, any change in padding (acquisition window), or changing to/from a high definition CT scan acquisition.
- To assess the difference in patient estimated effective radiation exposure (mSv) between the modified versus standard calcium scoring techniques.
- To assess the difference in patient estimated effective radiation exposure (mSv) of the entire CCTA study (plus calcium scoring) between groups.
- .

4. BACKGROUND AND SIGNIFICANCE:

4.1 Literature Review.

Cardiovascular disease is the leading cause of mortality and morbidity in the United States. The impact of coronary disease on our society has prompted increased emphasis on primary prevention. To identify the patients who would benefit the most from primary prevention, such as

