5.5 Study Methodology/Procedures

5.5 Methods:

The FOCUS-CCTA study will be a prospective, randomized single center single cohort study to evaluate the diagnostic and clinical implications of modified scan length calcium scoring versus the standard scan length calcium scoring in CCTAs using a MDCT scanner. Significant diagnostic and clinical implications include the quality of the study in the modified versus standard scan length; changes in the cardiac CT after evaluation of the modified or standard calcium scoring (These changes include: a change in mA by 50, any change in kV, any changes

in padding and changing to high definition.); cancellation of the study and a comparison of the radiation received by each patient.

CCTA Study Design:

Patients who are scheduled for CT coronary angiography for evaluation of clinically suspected coronary artery disease who are fifty years old or older without known coronary artery disease and without a previous calcium score will be prospectively included in this study. The indications for CT coronary angiography will be used in accordance with the ACCF/SCCT/ACR/AHA/ASE/ASNC/NASCI/SCAI/SCMR Appropriate Use Criteria for Cardiac Computed Tomography. Exclusion criteria will include patients who are not able to obtain angiography to include: previous anaphylactoid reaction to iodinated contrast material and renal insufficiency (verified by a renal panel within 30 days of the procedure).

In accordance with standard operating procedures for CCTA (joint Cardiology-Radiology program), patients will arrive to the cardiovascular preparation area (“Prep and Recovery”, Building 9A) and will receive a clinical assessment with vital signs by a physician and nursing staff. Patients without a contraindication to B-adrenergic blocking agents and/or calcium channel blocking agents (will be given a beta-blocker either by oral intake or intravenously prior to the exam to obtain a goal heart rate between 50-65 bpm). Once the patients are within this window they will be escorted to radiology, in accordance with standard CCTA policies. During the preparation time eligible patients will be consented by [name] and will be randomized at that time. The patient’s chart will have an envelope with it that describes which investigational arm the patient will be in. The radiologist and cardiologist will view the card in the envelope after making their initial decision on the parameters for the CCTA.

CT Protocol

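### The Aim 2 event is listed in two different ways, and the analysis table names neither the composite nor the margin on which the 81% power rests

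*Combined protocol and SAP*

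**What the plan says.** **The event.** Section 3 defines a significant change as any one of five: tube current by 50 mA, any change in tube potential, and then "change to/from retrospectively-gated CCTA, any change in padding (acquisition window), or changing to/from a high definition CT scan acquisition". Table 5.7.1 (Aim 2) lists the same five. Section 5.5 (Methods) and Section 5.8 (Secondary 1) list four: mA by 50, any kV change, any padding change, and a change to high definition. The Section 5.5 list runs "in padding and changing to high definition.); cancellation of the study"; the Section 5.8 list ends "any changes in padding and changing to high definition". Neither has a gating item.

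**The power statement.** Section 5.7.2 defines one composite, "event rate = any change in CCTA parameters". It says "This study will have 81% power to show that the event rate" with the reduced method is at least as low as with the full method. The assumptions are 50% in both groups, "that a difference of 20% points or less is unimportant", 79 per group and one-tailed alpha 0.05.

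**The analysis.** The Aim 2 row of Table 5.7.1 has five bullets, the note "All answered as yes/no", one treatment-group entry and one Fisher's exact test. It gives no composite line, margin, sidedness or multiplicity rule. Item 4 of Section 5.7.3 refers the analyst back to this table for the primary and secondary endpoints.

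**The concern.** Two things are left open that should be settled before data are seen.

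The first is who counts as an event. A patient whose only change is the gating mode, or leaving high definition, is an event under Section 3 and the table but is not on the list in Sections 5.5 and 5.8. Gating is not incidental: Section 4.1 names the type of ECG gating or triggering among the settings adjusted according to calcium.

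The second is which comparison answers Aim 2. The plan powers a non-inferiority claim on one composite, yet the only analysis text neither names that composite nor brings in the margin. An analyst following the table could combine the items or test them one by one. In either case the test is of no difference, which is not the claim that was powered.

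**Working it through.** **1. The four lists side by side**

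| Item | Section 3 | Table 5.7.1 | Section 5.5 | Section 5.8 |
|---|---|---|---|---|
| mA by 50 | yes | yes | yes | yes |
| any kV change | yes | yes | yes | yes |
| gating, to or from retrospective | yes | yes | not listed | not listed |
| any padding change | yes | yes | yes | yes |
| high definition | to or from | to or from | to only | to only |

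**2. The plan's own power figure.** Inputs from Section 5.7.2: p = 0.50 in both groups, margin 0.20, n = 79 per group, one-sided alpha 0.05 (z = 1.645).

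- Standard error = √(2 × 0.5 × 0.5 / 79) = 0.0796
- Power = Φ(0.20 / 0.0796 − 1.645) = Φ(2.514 − 1.645) = Φ(0.869) = 80.8%

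Exact binomial enumeration of the same Wald test gives 80.9%. The stated 81% is sound for one composite tested against the margin.

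**3. Does the choice of list change the sample size?** The documents give no gating-change rate. Assume a five-item composite of 50%, independent items, and a gating-change rate g from 2% to 20%. Without gating the composite rate is 1 − 0.5/(1 − g).

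| g (assumed) | composite without gating | power, 79 per group |
|---|---|---|
| 2% | 49.0% | 80.8% |
| 5% | 47.4% | 80.9% |
| 10% | 44.4% | 81.2% |
| 20% | 37.5% | 82.9% |

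Power hardly moves. The event rate falls by 1 to 12.5 points, which is 0.8 to 9.9 of 79 patients per group (79 × 0.01; 79 × 0.125).

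**4. How much imbalance the decision can absorb.** At 50% rates the one-sided 95% upper limit lies 1.645 × 0.0796 = 0.131 above the observed difference. Non-inferiority then needs an observed difference below 0.200 − 0.131 = 0.069. That is 5 of 79 patients (6.3%) but not 6 of 79 (7.6%). A handful of patients whose status depends on the list, if unevenly split, could therefore change the conclusion.

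**5. What the tabled test delivers.** Exact enumeration of a two-sided 5% Fisher test with 79 per group:

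- At 50% vs 50% it rejects in about 3% of trials.
- At 50% vs 70%, a true difference equal to the margin, it rejects in 67.6% and is non-significant in 100 − 67.6 = 32.4%.

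Taking non-significance as non-inferiority would thus pass a difference at the margin about 32% of the time, against the 5% intended.

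**6. If the items were tested separately.** With five independent tests at exactly 5%, the family-wise error is 1 − 0.95⁵ = 22.6%. Fisher's actual size at 79 per group is about 1.6% for an item rate of 5% and about 3% for rates of 10% to 50%. Under independence the family-wise error is then about 8% (1 − 0.984⁵) to 15% (1 − 0.9685⁵). Five equal independent items that make up a 50% composite would each have a rate of 1 − 0.5^(1/5) = 12.9%, so the 20-point margin would exceed the item rate and could not be transferred to single items.

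**The case against.** Four points can be made for the plan.

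- **The short lists may not be closed.** Sections 5.5 and 5.8 introduce their items as what the changes include, and Section 5.8 opens with any changes in the cardiac CT. Gating is therefore not expressly excluded. This stands, but then the endpoint section does not fix the event, and the narrowing of high definition to one direction remains.
- **The table may intend the composite.** A reader might infer that five separate tests replace the powered composite, so that the powered outcome is never analysed. The documents do not support that. Aim 1 pairs each outcome with its own test, whereas Aim 2 has five bullets and a single Fisher's test, and nothing says each item is tested alone. Section 3's any-of definition and the event in Section 5.7.2 fit a composite at least as well. The table's layout also passed through PDF extraction and is weak evidence either way. What remains is that the composite is not named and the margin is absent.
- **Few patients may be affected.** Reclassification needs gating or leaving high definition to be the only change, and a gating switch may well come with a padding change. If 5% to 10% of patients were in that position (an assumption) and the true rates were equal, a gap of 8 or more patients between arms would have probability 0.7% to 4.6%. This limits chance imbalance. It does not rule out a true difference between arms, which is what Aim 2 asks about.
- **The endpoint is secondary.** Section 5.7.2 ties the sample size to Aim 1, and step 3 shows that power is nearly unaffected. This stands and limits the severity.

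**Conclusion.** The point holds as two gaps in specification of a secondary endpoint, not as an error in the sample size. The mismatch between the lists is plain on the page. Its effect on the results cannot be sized from the documents; the 0.8 to 9.9 patients per group rests on assumed gating rates, independent items and a 50% composite.

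The second gap does not depend on those gating rates. Whether the items are combined or tested singly, a Fisher test of no difference does not establish non-inferiority within 20 points. The 81% belongs to a comparison that the analysis section does not state.

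A reader might also infer a false-positive rate of 22.6%. That figure applies only if the five items are tested separately, independently and at exactly 5%. Fisher's conservatism or positive correlation between settings of the same scan would lower it, and the documents do not say that separate testing is planned. The change should be made before analysis, but it does not call the design into question.

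**What to change.** - **Sections 5.5 and 5.8:** replace the four-item lists with the five items of Section 3, with gating and high definition counted in both directions. State in all four places whether the tube-current criterion means a change of at least 50 mA.
- **Table 5.7.1, Aim 2:** name any of the five changes (yes/no per patient) as the single Aim 2 outcome. Analyse it as the difference in proportions, reduced minus full, with a one-sided 95% upper confidence limit (the upper end of a two-sided 90% interval). Conclude non-inferiority if that limit is below the 20 points of Section 5.7.2.
- **Components:** report the five items descriptively by arm, without separate significance claims.

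The cost is wording in three sections and one confidence interval. No new data are needed: gating, padding, tube current and tube voltage are recorded before and after calcium scoring (Section 5.5.5). High definition is on the pre-imaging form (Section 5.5) and on the acquisition sheet, marked as decided before or after scoring.
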